3.2.3.3 Pregnancy Tests

Urine and serum pregnancy tests will be performed for females of childbearing potential.

Urine pregnancy test will be collected at Screening, in treatment period 1 at Visit 2 (Study baseline) and Visit 6 (Follow-up), in treatment period 2 at Visit 10 (Follow-up) and at premature discontinuation visit.

Serum pregnancy test will be collected at Screening, in treatment period 2 at Visit 6 (Baseline) and at premature discontinuation visit.

3.2.3.4 Vital signs

Vital signs (resting blood pressure, heart rate, and respiratory rate), body temperature and pulse oximetry will be measured.

Vital signs will be collected at Screening, in treatment period 1 at Visit 6 (Follow-up), in treatment period 2 at Visit 10 (Follow-up) and at premature discontinuation visit.

3.2.3.5 Physical Examination

A physical examination will be performed at the screening visit, in treatment period 1 at Visit 6 (Follow-up), in treatment period 2 at Visit 10 (Follow-up) and at premature discontinuation visit.

This evaluation will include examination of the following body systems: general appearance, eyes, ears, nose, throat, head and neck, chest and lungs, cardiovascular, abdomen, musculoskeletal, lymphatic, dermatological, neurological, and extremities.

3.2.3.6 Electrocardiogram Assessments

ECGs will be performed in triplicate at Screening, in treatment period 1 at Visit 6 (Follow-up), in treatment period 2 at Visit 10 (Follow-up) and at premature discontinuation visit.

A standard ECG will be obtained according to the Schedule of Events and recorded prior to blood sampling. Electrocardiograms will be read centrally for clinical significance and ECG intervals (PR, RR, QRS, QT, and QTcF using nomogram table), rate, rhythm, and other clinically significant abnormalities (e.g., left ventricular hypertrophy, pathological Q-waves).

ECG can be repeated if a subject develops a QTcF > 500 ms, or presents with an increase from study baseline > 60 ms, this can be a cause for discontinuation from the study.

The mean of the triplicate ECGs parameters will be derived. If no repeats of ECG are performed, then the single assessment received will be used in analysis; if ECG was only repeated twice, mean of the two assessments will be used; in case of ECG quadruplicate or more, only the first three

| Trevi Therapeutics, Inc. | | |
|--------------------------|------|---------------------------|
| TR12 | | Statistical Analysis Plan |
| | | |

assessments will be used for mean derivation. Unscheduled (including repeated) ECGs will not be included in the mean derivation.

3.2.3.7 Spirometry

Spirometry will be executed at Screening, in treatment period 1 at Visit 5 (day 21), in treatment period 2 at Visit 9 (day 21) and at premature discontinuation visit.

3.2.3.8 Diffusing capacity of the Lung for carbon monoxide (DLco)

DLco will be collected at Screening only.

3.2.3.9 Swallow Test

The Swallow Test will be assessed at Screening only.

3.2.3.10 Subjective Opiate Withdrawal Scale (SOWS)

Subjects will complete the SOWS on a daily basis for 14 days following the last dose of investigational product in each treatment period. Any subject discontinued from investigational product, prior to completion of the study, will also complete the SOWS daily for the 14 days following the last dose of investigational product (unless consent is withdrawn). The SOWS is a self-administered scale for grading opioid withdrawal symptoms.

The SOWS is provided in Protocol Appendix 4. Subjects will complete the SOWS via the study specific e-diary.

3.2.4 Exploratory Variables

As an additional exploratory analysis, a flag will be derived for 30%, 50% and 75% reduction from baseline in daytime cough counts.

Daytime cough frequency change from baseline (CfB) will be derived as follow:

Daytime cough frequency $CfB = (Day 22 \text{ cough frequency} - Study baseline cough frequency}) / Study baseline cough frequency) * 100.$

Daytime cough frequency CfB will then be categorized as follow:

- Daytime cough frequency CfB < 30%
- Daytime cough frequency $CfB \ge 30\%$ and <50%
- Daytime cough frequency $CfB \ge 50\%$ and <75%
- Daytime cough frequency $CfB \ge 75\%$

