11.1 Sample Size and Power

The planned sample size of 44 subjects for the final analysis (22 per sequence) provides at least 80% power to detect a 40% reduction in Day 22 daytime cough frequency (coughs per hour) with NAL ER tablet treatment compared to placebo tablets at the 5% significance level (2-sided). This assumes a CV of 1.00 in log-transformed Day 22 cough frequencies. The CV estimated from *Kelsall et al (2011)* data on chronic cough in patients without esophageal catheterization is 1.12; because Kelsall et al data was on 24-hour cough (including nighttime cough, a period of lower coughing rate) and were not taken in a sample of IPF patients only, it is believed that the CV will be lower than in Kelsall et al data. If the CV is larger than planned at 1.25, this sample size provides > 80% power to detect a 50% reduction from placebo to NAL ER. Alternatively, if the CV is 0.75, this sample size provides > 80% power to detect a 34% reduction from placebo to NAL ER.

A total of approximately 60 subjects will be randomized to ensure complete data from at least 44 subjects, assuming up to potentially a 26% dropout rate.

A statistical update on this Proof-of-Concept (POC) study may be conducted when a minimum of 12 subjects have completed both study periods for the purposes of determining whether POC can be established prior to complete enrollment of the study.

The analysis will be based on conditional power (CP). Futility will be declared if the CP is < 10%, while efficacy will be declared if the CP > 80% (*Mehta and Pocock, 2010*). If the CP is at least 41%, the number of subjects per treatment arm may be changed to recover the targeted power of 80%. If it is evident that the outcome is influenced by a baseline imbalance in disease characteristics then the baseline imbalance will be taken into account in supplemental analyses.

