4.11.5 Additional Exploratory Efficacy Evaluation

Responder analysis assessing 30%, 50% and 75% reduction in daytime cough counts

Exploratory variable described in this SAP section 3.2.4

4.12 Number and percentages of subjects with 30%, 50% and 75% reduction from baseline in daytime cough counts will be listed and presented by treatment group. Safety Evaluation

All safety summaries and analyses will be based upon the Safety Set as defined in Section 4.5.

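### The SAP promises responder rates at 30%, 50% and 75% reduction but derives only four mutually exclusive, wrongly signed bands, with no rule for turning them into cumulative rates (minor; exploratory analysis)

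*SAP*

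**What the plan says.** SAP 3.2.4 (Exploratory Variables) opens with the intention that "a flag will be derived for 30%, 50% and 75% reduction from baseline in daytime cough counts". It then changes quantity: "Daytime cough frequency change from baseline (CfB) will be derived as follow", followed by a formula equal to 100 × (Day 22 frequency − study baseline frequency) / study baseline frequency. Next, "Daytime cough frequency CfB will then be categorized as follow", with four categories. The lowest is "Daytime cough frequency CfB < 30" percent; the others are 30 to under 50, 50 to under 75, and 75 or more. None of the cut-offs has a minus sign.

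SAP 4.11.5 (Additional Exploratory Efficacy Evaluation) calls this a responder analysis, gives its source as "Exploratory variable described in this SAP section 3.2.4", and states that "Number and percentages of subjects with 30%, 50% and 75% reduction from baseline in daytime cough counts will be listed" and presented by treatment group.

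SAP 4.2.5 (Data Summaries) sets the default for categorical variables: frequencies and percentages per category, with any planned collapsing of categories described in the SAP text and the displays. Neither 3.2.4 nor 4.11.5 describes any collapsing for these bands.

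**The concern.** A responder rate at 30% normally means the share of patients whose reduction is at least 30%. The first sentence of 3.2.4 and the text of 4.11.5 fit that meaning. The one variable that 3.2.4 actually defines does not. A patient with a 60% reduction is a 30% responder in the first sense, but lies outside the 30 to under 50 band.

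A band percentage is a poor measure of response, because a patient who improves further leaves the band. An effective treatment moves patients into the band from below and out of it at the top, and the two flows can cancel. A table of band percentages labelled as 30% and 50% responder rates could therefore show little difference between treatments, or one in the wrong direction, while the cumulative rates show a clear benefit.

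Two further faults sit in the same lines. The change is negative for a reduction, so the positive cut-offs applied literally classify worsening. And the text speaks of counts where the formula uses frequency.

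**Working it through.** **Inputs from the documents** (Protocol 11.1; SAP 4.14 repeats the planning case)
- 44 completers in a two-period crossover, two-sided 5% level, 40% reduction versus placebo: "The planned sample size of 44 subjects for the final analysis (22 per sequence) provides at least 80% power to detect a 40% reduction". Log ratio ln 0.6 = −0.511.
- CV 1.00, read as log SD σ = √ln(1 + 1.00²) = √0.693 = 0.833.

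**Inputs assumed** (not in the documents)
- SD of log(Day 22 / baseline) = 0.833 × √2 = 1.177. This treats 0.833 as the SD of each measurement and the two measurements as uncorrelated.
- No change from baseline on placebo.
- Log ratio normally distributed.

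**Step 1. Reproduce the plan's power.** SE = 0.833 × √(2/44) = 0.1775, and 0.511 / 0.1775 = 2.878. Normal approximation: Φ(2.878 − 1.960) = 82.1%. Noncentral t with 42 df: 80.3%. Both agree with the stated minimum of 80%. The other two scenarios in Protocol 11.1 also hold: CV 1.25 with a 50% reduction gives 91.8% (t: 90.6%), and CV 0.75 with a 34% reduction gives 83.1% (t: 81.3%). Taking the log SD itself as 1.00 gives only 66.9%, so the reading of the CV used here is the one that matches the plan.

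**Step 2. Cumulative rates.** P(reduction ≥ r) = Φ[(ln(1 − r) − μ) / 1.177], with μ = −0.511 on NAL ER and 0 on placebo.
- r = 30%: NAL ER Φ[(−0.357 + 0.511) / 1.177] = Φ(0.131) = 55.2%; placebo Φ(−0.303) = 38.1%.
- r = 50%: NAL ER Φ[(−0.693 + 0.511) / 1.177] = Φ(−0.155) = 43.8%; placebo Φ(−0.589) = 27.8%.
- r = 75%: NAL ER Φ[(−1.386 + 0.511) / 1.177] = Φ(−0.744) = 22.9%; placebo Φ(−1.177) = 12.0%.

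**Step 3. Bands, signs read as reductions.** Subtract adjacent cumulative rates, for example 55.2 − 43.8 = 11.4. Entries are NAL ER vs placebo in %, with the difference in percentage points.

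| Threshold | Cumulative | Difference | Band | Difference |
|---|---|---|---|---|
| 30% | 55.2 vs 38.1 | 17.1 | 11.4 vs 10.3 | 1.1 |
| 50% | 43.8 vs 27.8 | 16.0 | 21.0 vs 15.9 | 5.1 |
| 75% | 22.9 vs 12.0 | 10.9 | 22.9 vs 12.0 | 10.9 |

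**Step 4. Sensitivity.** Vary the log-change SD from 0.4 to 1.41 and the placebo reduction from 0 to 30%, keeping the treatments ln 0.6 apart.
- 30%: the band difference runs from −6.9 to +18.1 points; the cumulative difference from +14.1 to +47.7.
- 50%: the band difference runs from about +2 to +38 points; the cumulative difference from about +14 to +47.
- Both ends of the 30% band range occur at SD 0.4. With no placebo change, the band is 32.6 vs 14.5 and the cumulative rate 65.0 vs 18.6. With a 30% placebo reduction, the band is 23.1 vs 30.0 and the cumulative rate 89.9 vs 50.0.

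**Step 5. Bands exactly as printed.** A 60% reduction has CfB = −60 and falls in the category below 30, as does every patient who improves. In the case of Step 2 the four categories hold 74.4 vs 58.8, 3.7 vs 4.7, 3.7 vs 4.8 and 18.2 vs 31.7 (NAL ER vs placebo, %). The upper three count patients whose cough rose by 30% or more.

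**The case against.** The strongest reply is that the SAP nowhere says the band percentages are the responder rates. It promises a flag, and it promises the number of patients with each reduction. A patient with an 80% reduction is naturally also one with a 30% reduction, so a programmer may well produce cumulative rates. Correctly signed bands lose no information either: summed upward they return the cumulative rates exactly, and SAP 4.2.4 lists all original and derived parameters. This stands, and it limits the harm to the case where bands are labelled as rates. It does not remove the conflict, because 4.11.5 points to the variable in 3.2.4, only the bands are defined there, and the collapsing that 4.2.5 says will be described is not.

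The sizes can also be challenged. Protocol 11.1 gives a CV for Day 22 values, not an SD of change, and SAP 4.11.2 expects repeated measurements to correlate, so 1.177 may be too large. Zero placebo change is likewise an assumption. Both challenges are fair, and the range in Step 4 is there for that reason.

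A reader might infer from the wording on counts that shorter waking time under a sedating drug would create responders. The documents do not support that. The formula and all four categories use frequency, the primary variable in SAP 3.2.1.1 is coughs per recorded waking hour, and no change in counts is derived. The mismatch is one of wording.

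**Conclusion.** The point holds as a conflict between what the SAP promises (responder rates) and what it derives (disjoint bands with the wrong sign and no collapsing rule). If band percentages are reported as the rates, then with the signs read as reductions, a log-change SD of 1.177 and no placebo change, the treatment difference falls from about 17 points to 1 at 30% and from 16 to 5 at 50%.

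A reader might infer that the plan omits the best responders as a matter of rule and so nearly erases the treatment difference. That goes too far. The omission depends on how the tables are built. Near-disappearance fits the 30% band in the case above, but not the 50% band, which keeps about a third of its difference (5.1 / 16.0), and the 75% rate is the same either way. Under other assumptions in the range the 30% band keeps up to 18 points, or reverses by about 7.

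Severity is minor. The analysis is exploratory and descriptive, it is not among the endpoints in Protocol 8.1, and the primary analysis is untouched.

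**What to change.** - In SAP 3.2.4, derive three nested yes/no flags from daytime cough frequency in coughs per hour: CfB ≤ −30%, CfB ≤ −50% and CfB ≤ −75%.
- In SAP 4.11.5, tabulate these three flags by treatment as the responder rates.
- Keep the four bands only as a supporting distribution, with signs corrected and labelled as bands.
- In both sections, replace cough counts by cough frequency, to match the formula.

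The cost is a few lines of SAP text and three derived flags. No new data are needed and no other analysis changes. The definition should be settled before general unblinding, so that the choice between bands and cumulative rates cannot depend on the results.

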11.3.2 Missing Data

Missing or dropout data will not be imputed for the purpose of data analysis except for binary "responder" type of efficacy endpoints.

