Daytime cough frequency = ((total cough events for a session not within Sleep, Device Not Attached, Recording Ended Early, Flagged Area event periods) / (recording length in seconds - Sleep, Device Not Attached, Flagged Area event period durations)) x 3600. A session is defined as that 24-hour period when cough recording is taking place for an individual subject. For a session with 'Recording Ended Early', the recording early end datetime will be the end datetime for the session. No events will be collected after the recording early end datetime.

Recording of daytime cough frequency is expected in treatment period 1 at Visit 2 (Study baseline: starting on day -1 and ending at day 1 prior to first IMP intake) and Visit 5 (starting on day 21 and ending on day 22), and in treatment period 2 at Visit 6 (Baseline: starting on day -1 and ending at day 1 prior to first IMP intake) and Visit 9 (starting on day 21 and ending on day 22).

A 24-hour recording is required per protocol at each appropriate visit. All recordings considered valid per Vitalograph[®] quality assessment will be used in analysis, irrespective of actual duration. Cough frequency will be computed based on the actual recording duration.

For the primary endpoint analysis, daytime cough frequency will be log transformed on the natural log scale; ratios will be then calculated per subject per period as log (Visit cough / Study baseline cough) which would represent, upon back transformation and subtraction from 100%, a percent reduction in daytime cough frequency versus study baseline.

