4.2.5 Data Summaries

Subject disposition, Demographics, Medical History, Treatment Exposure and Treatment Compliance tables will be summarized by sequence (see definition in section 4.2.1).

In efficacy and safety tables (including concomitant medications), results will be summarized under the actual treatment received (NAL-ER or Placebo) independently whether the NAL-ER (and Placebo) was received in Treatment Period 1 or 2. In other words, summaries will be presented by treatment received.

In most instances, the baseline visit for Treatment Period 2 will occur on the same calendar day as the Follow-up Visit 6 for Treatment Period 1; in any case, Visit 6 results will be used as Follow-up for Treatment Period 1, while the baseline for the Treatment Period 2 will be the study baseline (taking into account baseline definition from section 4.2.3).

Continuous data will be summarized in terms of the number of subjects with non-missing values, mean, standard deviation (SD), median, minimum and maximum, unless otherwise stated.

The following rules will apply to all descriptive statistic displays, where 'd' denotes the decimal places in the original reported value:

- n (number of non-missing observations): 0 decimal places (d.p.)
- Mean: d + 1 d.p.
- SD: d + 2 d.p.
- Median: d + 1 d.p.
- Minimum: d
- Maximum: d
- Statistics in percentage: 1 d.p.
- Confidence Intervals (CIs): d + 1 d.p.
- A maximum of 3 decimal places will be displayed.

All CIs will be reported as 2-sided and will be assessed at α =0.05 significance level unless otherwise stated.

Categorical data will be summarized in terms of the number of subjects providing data at the relevant time point (n), frequency counts and percentages. The denominator for the proportion will be based on the number of subjects who provided non-missing responses to the categorical variable. Any planned collapsing of categories will be detailed in the SAP text and the data displays.

Percentages will be presented to one decimal place. Percentages will not be presented for zero counts. Percentages will be calculated using n as the denominator.

In general, for categorical variables showing multiple possible categories, these will be displayed following the within variable logic criteria; where such a logic criterium does not exist (example: gender, race, AE SOC, AE PT), categories will be displayed by overall descending frequencies.

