4.11.1.2 Adjustments for Covariates

The primary efficacy analysis will be adjusted for the following covariates:

- 1. Subject (random repeated effect)
- 2. Study baseline measure of primary efficacy variable
- 4.11.1.3 Handling of Dropouts or Missing Data

Missing or dropout data will not be imputed for the purpose of data analysis.

The Primary Efficacy Analysis will be performed on the FAS and on Completers Analysis Set as sensitivity analysis; there will not be imputation of primary or secondary efficacy endpoints eventually missing at a specific timepoint.

Rules to handle with AEs partial onset and dates will be detailed in section 4.11.1.

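### SAP 3.2.4 applies positive cut-offs to a signed change in which reductions are negative, so every improved subject lands in the lowest responder band

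*SAP*

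**What the plan says.** SAP 3.2.4 opens with its purpose: "a flag will be derived for 30%, 50% and 75% reduction from baseline in daytime cough counts". It then defines CfB as the Day 22 daytime cough frequency minus the study baseline frequency, divided by the study baseline frequency and multiplied by 100. Four bands of CfB follow. The lowest is "Daytime cough frequency CfB < 30" (per cent); the others are 30 to below 50, 50 to below 75, and 75 or more. No minus sign, absolute value or redefinition as a reduction comes between the formula and the bands.

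SAP 4.11.5 names the output, "Responder analysis assessing 30%, 50% and 75% reduction in daytime cough counts", and refers to 3.2.4 for the variable. The sentence promising numbers and percentages of subjects by treatment has run into the heading of 4.12. It also speaks of reductions and gives no sign rule.

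SAP 3.2.1.1 does spell out a conversion for the primary variable. The log ratio to study baseline gives, "upon back transformation and subtraction from 100%, a percent reduction in daytime cough frequency versus study baseline". Section 3.2.4 has no such step.

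On missing data, Protocol 11.3.2 says "Missing or dropout data will not be imputed for the purpose of data analysis except for binary" responder-type efficacy endpoints, and names no method for that exception. SAP 4.11.1.3 says "Missing or dropout data will not be imputed for the purpose of data analysis" and has no exception. SAP 4.2.5 adds the general rule for percentages: "The denominator for the proportion will be based on the number of subjects who provided non-missing responses to the categorical variable".

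**The concern.** The derivation runs the opposite way to its stated purpose. A fall in cough gives a negative CfB, and a negative number can never reach a cut-off of +30, +50 or +75. The bands meant for responders can therefore be filled only by subjects who got worse, and the band meant for non-responders takes in everyone who improved.

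Section 3.2.4 is the text a programmer works from, and 4.11.5 sends the reader there. The programmer either follows it and produces a wrong table, or reverses the sign without a written instruction. SAP 4.1 requires independent checking of outputs, but a checker who re-derives the table from the same text would get the same wrong result.

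At stake is the responder table and any description of the results drawn from it. The primary analysis does not use these bands.

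**Working it through.** **Inputs.** The formula, the four bands and the purpose come from SAP 3.2.4. The documents state no responder figure to reproduce. The cough rates below are chosen for illustration and are not trial data; the result does not depend on the baseline chosen.

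**Algebra.** Write r = Day 22 / study baseline, so CfB = 100 × (r − 1).

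- If cough falls, 0 ≤ r < 1, so −100 ≤ CfB < 0. This is always below 30.
- CfB ≥ 30, 50 or 75 requires r ≥ 1.30, 1.50 or 1.75.
- A reduction of at least 30%, 50% or 75% requires r ≤ 0.70, 0.50 or 0.25.

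The two sets of conditions do not overlap.

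**Worked example, baseline 30 coughs/h.** Percent reduction is 100 × (baseline − Day 22)/baseline, which is −CfB.

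| Day 22 (per h) | CfB (%) | Band as written | Percent reduction | Band on reduction |
|---|---|---|---|---|
| 6 | −80 | <30 | 80 | ≥75 |
| 12 | −60 | <30 | 60 | 50 to <75 |
| 18 | −40 | <30 | 40 | 30 to <50 |
| 27 | −10 | <30 | 10 | <30 |
| 30 | 0 | <30 | 0 | <30 |
| 36 | +20 | <30 | −20 | <30 |
| 42 | +40 | 30 to <50 | −40 | <30 |
| 48 | +60 | 50 to <75 | −60 | <30 |
| 54 | +80 | ≥75 | −80 | <30 |

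For example, (6 − 30)/30 × 100 = −80 and (54 − 30)/30 × 100 = +80. As written, an 80% fall is placed with no change, and an 80% rise fills the top band.

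**Boundaries, baseline 20 coughs/h.** Day 22 values of 14, 10 and 5 give CfB of −30, −50 and −75, and all fall in the lowest band. Values of 26, 30 and 35 give +30, +50 and +75 and enter the second, third and top bands.

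**Simulation.** In 100,000 random pairs with Day 22 below baseline, every pair fell in the lowest band, as the algebra requires.

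**Could text extraction explain it?** The formula has stray typesetting characters, but the order of subtraction is clear. Restoring lost minus signs would not help: at or above −30 and below −50 is an empty set. Restoring lost absolute-value bars would not help either, since a 60% rise would then share a band with a 60% fall. The bands make sense only on percent reduction, which 3.2.4 never defines.

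**The case against.** The strongest reply is that nobody would be misled. Both 3.2.4 and 4.11.5 say reduction, a table of reductions filled with worsened subjects would look absurd, and SAP 4.1 requires outputs to be checked for consistency. On this view it is a labelling slip with one sensible reading. The intent is indeed clear, which makes the correction uncontroversial. But clear intent does not turn an operative derivation into one that works as written.

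Two narrower replies stand. The CfB formula is itself an ordinary percent change; the fault is in pairing it with these bands, and rewriting the bands would serve as well as replacing the formula. Also, the SAP has no settled percent-reduction convention: the back-transformation code in 4.11.2, 100 × (exp(estimate) − 1), is likewise negative for a reduction. The contrast with 3.2.1.1 therefore shows only that the conversion was available, not that 3.2.4 broke a uniform rule.

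On missing data, the protocol lists no responder endpoint, so its exception attaches to nothing it names, and the SAP's general rules can be read as covering the table: no imputation and non-missing denominators. That has force, and it keeps this point secondary. The two documents still give different instructions for the same type of endpoint. The Full Analysis Set in 4.5.2 requires only one post-baseline primary assessment, so a subject can be in it with no Day 22 value on one treatment.

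**Conclusion.** The concern holds. As written, 3.2.4 puts every improved subject in the lowest band and reserves the upper bands for rises of at least 30%. Nothing elsewhere in the SAP corrects it. The conclusion is algebraic and rests on no assumption about the data, only on reading the formula and bands as printed.

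Its reach is limited. No hypothesis test, sample size or stopping decision in the documents uses these bands, and the primary log-ratio model is unaffected. It should be corrected because the error is certain and the table cannot be right if the text is followed. The missing-data difference is a separate, minor inconsistency and does not bear on this conclusion.

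**What to change.** In SAP 3.2.4, define percent reduction = 100 × (study baseline − Day 22)/study baseline and apply the existing cut-offs to it. Equivalently, keep CfB and rewrite the bands as above −30; above −50 up to −30; above −75 up to −50; and −75 or lower.

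In SAP 4.11.5, state that the number and percentage of subjects with a reduction of ≥30%, ≥50% and ≥75% will be shown by treatment. These are the sums of the top three bands, the top two, and the top one.

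Separately, add one sentence reconciling Protocol 11.3.2 with SAP 4.11.1.3 and 4.2.5: whether the responder exception applies to this table, by what method, and with what denominator. One option, which is not the protocol's stated rule, is to count a subject who took a treatment but has no Day 22 recording for it as a non-responder on that treatment.

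The cost is one formula and two sentences. No new data are needed and the primary analysis does not change.
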